## Visit 3: BEGIN FIRST TREATMENT (WEEK 0)

At this Randomization Visit, the 2-week sleep diary will be reviewed for definitive eligibility before the participant is randomized to treatment. Baseline questionnaires will be determined at this visit. Baseline subjective and actigraphic sleep measures will be determined from the last 7 days of this 2-week period. Baseline pre-treatment symptom measures will be determined from the Randomization Visit. If the subject did not wear the actiwatch over 80% of the time during the two weeks before randomization, or if their data is missing (e.g. due to device malfunction), the actigraph will be sent back to the subject and he or she will be asked to repeat the baseline data collection period.

Eligible participants will be randomized in a 1:1 ratio for the first 4-week period of placebo or suvorexant. Subjects will be mailed 14 days of the 10 mg dose of study medication following this visit.

Subjects will also be mailed 42 additional pills of the 10 mg dose for use in weeks 1 to 3. Subjects will also be mailed actiwatches, and will be instructed to wear these during the two weeks leading up to Visit 5.

# Visit 4: INTERIM PHONE CONTACT 1 (WEEK 1)

The study physician will call the participant to inquire about efficacy and adverse events. If the 10 mg dose is well tolerated but not effective, the dose can be increased to 20 mg. The study physician will instruct the participant to take either one pill (10 mg) or two pills (20 mg) nightly over the next three weeks.

### Visit 6: BEGIN SECOND TREATMENT (WEEK 6)

After the 2-week washout phase all participants will be crossed over to the other treatment for the second 4-week treatment phase. Subjects will be mailed 14 days of the 10 mg dose of either suvorexant or placebo following this visit.

Subjects will also be mailed 42 additional pills of the 10 mg dose for use in weeks 7 to 9. Subjects will also be mailed actiwatches, and will be instructed to wear these during the two weeks leading up to Visit 8.

## Visit 7: INTERIM PHONE CONTACT 2 (WEEK 7)

The study physician will call the participant to inquire about efficacy and adverse events. If the 10 mg dose is well tolerated but not effective, the dose can be increased to 20 mg. The study physician will instruct the participant to take either one pill (10 mg) or two pills (20 mg) nightly over the next three weeks.

## Visit 8: END SECOND TREATMENT (WEEK 10)

During this final virtual study visit, participants will meet with a study physician. The physician will assess the participant on the Clinical Global Impression-Improvement (CGI-I) scale and will also inquire about any adverse events experienced. Questionnaires will also be administered at this visit. Subjects will be asked to mail actiwatches back to the study team after the visit.

#### **Compensation:**

Subjects will be compensated \$50 for study visit 2 and for virtual visits 3-8 (\$25/visit). Subjects will receive a completion bonus when they have completed the study in its entirety (\$50). The total possible compensation is \$250.

See below for the Table of Procedures and Study Flowchart.

#### **Table of Procedures:**

		Screening Period		Treatment Period 1			Treatment Period 2		
Visit		V1/ Initial Screening	V2/ Screening	V3/ Randomization	V4/ Interim phone Contact 1	V5/ End of 1st Treatment	V6/ Begin 2nd Treatment	V7/ Interim phone Contact 1	V8/ End of 2nd Treatment
Study Week		-4	-2	0	1	4	6	7	10
Visit Location		Phone	Zoom	Zoom	Phone	Zoom	Zoom	Phone	zOOM
General/ Screening Assessment	Sleep/medical/mental health phone screening and verbal consent	x							
	Written Informed Consent		x						
	Eligibility Criteria		x	x					
	Medical History		x						
	Urine hCG		x						
	Concomitant Medication		x	x	x	x	x	x	x
	ISI	x		x		x			x
	PHQ-9	x							
	STOP-BANG	x							
	CH-RLSq		x						
	BDI			x		x			x
	IRLS	x		x		x			x
	CGI-I					x			x
	PGI-I					x			x
	DBAS			x					
Sleep Assessment	Sleep Diaries (administer/review)	xª		xb		xb			xb
	Actigraphy (administer/download)			xb		xb			xb
	PSQI			x		x			x
Dispensing of Actiwatches in mail	Given to subject		x		x			x	
	Returned by subjects			x		x			x
Medication Dispensed in Mail				x	x		x	x	
Safety Assessment/ Adverse Event Reporting					x	x		x	x
Medication Adherence					x	x		x	x
Study procedures completed between study events: a = daily for 2 wks following visit, b = daily for 2 wks prior to visit									

hCG = Human chorionic gonadotropin, ISI = Insomnia Severity Index, PHQ-9 = Patient Health Questionnaire, CH-RLSq = Cambridge-Hopkins RLS questionnaire, BDI = Beck Depression Inventory, IRLS = International Restless Legs Scale, CGI-I = Clinician Global Impression of Improvement, PGI-I = Patient Global Impression of Improvement, DBAS = Dysfunctional Beliefs and Attitudes about Sleep, PSQI = Pittsburgh Sleep Quality Index.

#### **Study Flowchart:**

## VI. STUDY MEDICATION AND SUPPLIES

### **Study Treatments:**

The study medication will consist of 10 mg suvorexant tablets, or matching placebo, prepared in identically appearing capsules by Merck and distributed by the MGH Clinical Trials Pharmacy. The medication will be titrated and distributed according to the following schedule:

Double-Blind Suvorexant / Placebo Dosing							
	Group:						
	Treatment →	Placebo ->					
Week	Placebo	Treatment					
0	One 10 mg suvorexant tablet	One 10 mg placebo tablet					
1-3	One or two 10 mg suvorexant tablets	One or two 10 mg placebo tablets					
6	One 10 mg placebo tablet	One 10 mg suvorexant tablet					
7-9	One or two 10 mg placebo tablets	One or two 10 mg suvorexant tablets					

## **Dispensing Schedule:**

Subjects will be instructed to take the study medication within 30 minutes of going to bed and will be informed during the consent process that they may be receiving drug or placebo at different points during the study. Participants will be instructed to take 10 mg nightly for the first 7 days. If the 10-mg dose is well tolerated but not effective after one week of treatment, as determined by the one-week phone visit, the dose can be increased to 20 mg (i.e. two 10 mg pills). This will be repeated at the 7-week phone call.

## **Study Medication Packaging:**

Medication will be prepared and packaged by the MGH Clinical Trials Pharmacy. The medication will be dispensed in bottles containing enough for 14 days of medication after the Randomization visit, as well as enough for weeks 1-3. After the 6-week visit, a 14-day supply will again be dispensed, as well as a supply sufficient for weeks 7-9. Bottles will be labeled with the patient

name and ID and the dosing information. Bottles will be clearly labeled as containing 10 mg matching placebo or suvorexant tablets.

Subjects will be dispensed the appropriate number of tablets needed until the next medication dispensing date. Study medication should be stored at room temperature 15-30°C (59-86°F), be protected from moisture, and be maintained in a secure area.

## **Study Medication Accountability and Compliance:**

Starting at the Randomization Visit, study medication will be dispensed to each subject with instructions to save all unused study medication in order to assess compliance. Participants will be required to show the study team over video how much medication is remaining. Additional bottles will be dispensed to each subject as needed.

All study medication dispensed by the investigator or designee will be accounted for throughout the study. Information about subject dosing and compliance will be recorded in the subject's study records. Subjects who are noncompliant with medications (according to pill counts and diaries) may be removed from the study at the discretion of the investigators.

The investigator agrees not to allow access to the study medication to any person except those named as sub-investigator(s) or clinical care staff and dispense only to qualified subjects participating in the study.

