## STATISTICAL METHODS

Efficacy variables will be analyzed using an analysis of variance model with treatment, sequence, and period as fixed effects and subject within sequence as a random effect. Least squares (LS) mean treatment difference will be calculated from the model. Diagnostic methods will be used for all variables to assess their distributional assumptions and to examine potential outlying or influential data points. This analytical method will similarly be used to assess secondary outcomes. Within-treatment changes from baseline will also be evaluated using a paired t-test for the primary and secondary efficacy variables of change from baseline in total sleep time, wake after sleep onset, and ISI.

The primary outcome analysis will use the intention-to-treat principle and include all participants who received at least one dose of study medication and completed at least one week of sleep diaries following randomization.

Per-protocol analyses will be repeated on the subgroup of subjects that achieve 85% medication adherence based on the number of pills returned at the end of study. Variables related to subjective total sleep time will be determined by Pearson correlation and simple regression analysis using weighted least squares. A two-sided P value <0.05 will be considered significant.

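### Discretionary removal of noncompliant participants, with no outcome collection afterwards, undermines the intention-to-treat primary analysis in effect

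*Combined protocol and SAP*

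**What the plan says.** Section VI, Study Medication Accountability and Compliance: "Subjects who are noncompliant with medications (according to pill counts and diaries) may be removed from the study at the discretion of the investigators". The section gives no level of adherence that triggers removal, no timing, and no follow-up for those removed.

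Section IX, Statistical Methods: "The primary outcome analysis will use the intention-to-treat principle and include all participants who received at least one dose of study medication", with the further condition that they "completed at least one week of sleep diaries following randomization". Adherence is handled separately: "Per-protocol analyses will be repeated on the subgroup of subjects that achieve 85% medication adherence based on the number of pills returned". The primary model is a crossover analysis of variance with "treatment, sequence, and period as fixed effects and subject within sequence as a random effect". No method for missing outcome data is stated.

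For the first treatment period, section V (Visit 3) has participants receive actiwatches that they "will be instructed to wear these during the two weeks leading up to Visit 5". Visit 6 repeats this for Visit 8. The Table of Procedures schedules diaries for the same two windows and lists an adherence check at Visits 4, 5, 7 and 8.

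**The concern.** Intention-to-treat requires that outcomes be collected whatever the participant does with the tablets. A rule that ends participation because of poor adherence stops the outcome data before the analysis begins, so the primary comparison can become partly selected on adherence whatever the analysis section promises.

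The selection need not be neutral. Participants may stop tablets because they feel no benefit or because of effects such as the next-day drowsiness listed in section VII. The physician who calls at weeks 1 and 7 asks about efficacy and adverse events at the same contacts where adherence is checked. Blinding prevents deliberate selection by treatment, but it does not prevent selection through how the treatment works or is tolerated. Such removals would also bring the primary set closer to the 85% adherence set, so agreement between the two analyses would be less reassuring than it looks.

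**Working it through.** **1. The plan's own sample size.** Power/Sample Size gives an effect size of 0.58, 90% power and 34 completers; Statistical Methods gives two-sided 0.05. Take 0.58 as the standardised within-participant difference.
- Normal approximation: ((1.960 + 1.282)/0.58)² = 31.2, so 32.
- Noncentral t with noncentrality 0.58√n: power is 89.8% at n = 33 and 90.7% at n = 34 (90.6% with n − 2 degrees of freedom).

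The figure of 34 is reproduced. Randomising 44 allows 10 losses from any cause (10/44 = 22.7%). No share of these is attributed to removal for noncompliance.

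**2. What each removal time costs.** This sets the adherence checks against the recording windows (weeks 2–4 and 8–10).

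| Removed at | Actigraphy after baseline | Primary set (one diary week) | Within-participant contrast |
|---|---|---|---|
| Visit 4 (week 1) | none | likely fails: no diary scheduled yet | lost |
| Visit 5 (week 4) or 7 (week 7) | period 1 only | can be met | lost |
| Visit 8 (week 10) | both periods | can be met | kept |

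**3. What period-1-only data are worth.** Fitted with a random participant effect, the model can use a single period. Take 34 complete pairs plus 10 participants with period 1 only (5 per sequence), total variance 1 and an assumed within-participant correlation ρ. With pairs alone, the variance of the treatment difference is 2(1 − ρ)/34. Generalised least squares with treatment, period and sequence gives:

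| ρ (assumed) | Pairs only | Pairs + 10 singles | Reduction |
|---|---|---|---|
| 0.3 | 0.0412 | 0.0379 | 8% |
| 0.5 | 0.0294 | 0.0277 | 6% |
| 0.7 | 0.0176 | 0.0170 | 3% |

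Without the sequence term the reductions are 9%, 7% and 4%. The data count, but little.

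**4. Possible bias, as an illustration.** Let k of 44 be removed, let δ be the mean effect they would have shown, and let the others show the planning difference of 34.7 minutes. Then

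effect in all randomised = [34.7(44 − k) + δk]/44.

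With δ = 0:
- k = 2: 34.7 × 42/44 = 33.1 minutes
- k = 4: 34.7 × 40/44 = 31.5 minutes
- k = 6: 34.7 × 38/44 = 30.0 minutes
- k = 10: 34.7 × 34/44 = 26.8 minutes

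Complete pairs would show about 34.7 in each case. The difference is (k/44)(34.7 − δ). It is zero if δ = 34.7 and changes sign if δ is larger. The documents give neither k nor δ.

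**5. Precision.** The first 10 losses are already allowed for. Beyond that, power (n − 2 degrees of freedom) falls from 90.6% at 34 pairs to 88.8% at 32, 86.6% at 30 and 84.0% at 28. The allowance covers numbers, not selection.

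**The case against.** Much can be said for the plan.

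- **A reader might infer that the two sections contradict each other.** They do not in words. The clause is permissive and concerns leaving the study, while Statistical Methods still admits any dosed participant with a week of diaries. No sentence excludes removed participants from the analysis. This stands: the conflict is one of effect.
- **A reader might infer that every removal destroys the within-participant contrast and all the participant's data.** Removal at Visit 8 costs nothing, and after Visit 5 or 7 the period-1 data stay in the model. This stands too.
- **Removal at week 1 is the least supported case.** The clause relies on pill counts and diaries. Counts are shown over video, but Visits 4 and 7 are by phone, and no diary is scheduled by week 1. Even so, the Table of Procedures lists an adherence check at both visits, so removal then is not ruled out.
- **A reader might infer that the effect will be overstated by a definite percentage.** The documents do not support this. A placebo-first participant removed for lack of benefit never reaches suvorexant, and losing someone who might have gained could lower the estimate. A suvorexant-first participant removed at Visit 5 leaves a poor result in the model. The net direction depends on removal rates by treatment, which are not given.
- **The investigators do not see the endpoint.** They are blinded, the watches are mailed back and a technician scores them. Their judgement can be informed by reported benefit and tolerability, not by actigraphic sleep time.
- **A reader might infer that the per-protocol comparison becomes useless.** That goes too far: removal is optional, so participants below 85% who stay in can still make the two analyses differ.

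What does not stand is the view that this is only part of the plan's general silence on missing data. Here a stated rule itself creates missing outcomes, and does so on adherence.

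**Conclusion.** The concern holds in a limited form. Following the compliance clause as written undermines the intention-to-treat analysis as written, because outcomes cease for participants chosen on adherence, by judgement and without a threshold. The cost depends on timing: the whole primary outcome at week 1, the second period at Visits 5 and 7, and nothing at Visit 8.

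Bias in the total sleep time effect is possible but is not established in direction or size. The range of 33.1 to 26.8 minutes against about 34.7 rests wholly on two assumptions: 2 to 10 removals among 44, and no effect in those removed. It shows what could be at stake and is not an estimate. If noncompliance were unrelated to response, the loss would be mainly of precision. The sample-size figure of 34 is not in dispute here.

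**What to change.** Amend Study Medication Accountability and Compliance to state that noncompliance alone does not end study participation or outcome collection. The actigraphy, diaries and questionnaires already scheduled for Visits 5 and 8 would still be collected and analysed as randomised under Statistical Methods. Noncompliance would be recorded and used only to define the 85% per-protocol set.

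This separates taking the study drug from staying under observation. Decisions on study drug and stops for safety remain with the investigators and are not changed.

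The cost is a short amendment and the follow-up of a few poor adherers, with no new procedure. Keeping them may make the observed effect smaller, but that is the effect an intention-to-treat analysis is meant to report.

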## **Randomization:**

Randomization will be used to avoid bias in the assignment of subjects to treatment, to increase the likelihood that known and unknown subject attributes (e.g., demographics and baseline characteristics) are evenly balanced across treatment groups, and to enhance the validity of statistical comparisons across treatment groups. Blinded treatment will be used to reduce potential bias during data collection and evaluation of clinical endpoints.

At the Screening Visit, subjects will be assigned a 3-digit subject number, in ascending sequential order beginning with 001. The subject number will be retained by the subject for the duration of the study. The MGH Clinical Trials Pharmacy will provide and maintain randomization and blinding. Subjects will be randomized to the two crossover groups in a 1:1 ratio. Subject and investigator will be blinded to treatment assignment. Subjects will be randomized sequentially as they qualify for the study.

## Blinding:

The randomization code will be maintained by the MGH Clinical Trials Pharmacy and will not be revealed to study subjects, investigators or blinded clinical staff until all subjects have completed and the database has been finalized.

Under normal circumstances, the blind should not be broken. The blind should be broken only if specific treatment would be dictated by knowing the treatment status of the subject. Individual code breaks by the investigator will normally result in withdrawal of the subject from the trial. The date, time and reason for the unblinding must be documented in the study files.

## VII. RISKS AND DISCOMFORTS

## **Medication Side Effects and Adverse Events:**

The package insert for suvorexant includes warnings and precautions related to the following side effects or adverse events: sleepiness during the day, not thinking clearly; acting strangely, confused, or upset; "sleep-walking" or doing other activities during sleep, such as eating, talking, having sex, or driving a car; temporary weakness in your legs or inability to move or talk, cataplexy; and diarrhea, dry mouth, upper respiratory tract infection, headache, next-day drowsiness, dizziness, abnormal dreams, and cough.

Subjects will be informed of the risks associated with consuming alcohol while taking suvorexant, both at the time of consent and throughout the study. Subjects will be advised not to consume alcohol in combination with suvorexant due to additive psychomotor effects.

Subjects will be assessed for depression and suicidal ideation at each study visit, using the Beck Depression Inventory (BDI).

All adverse events that occur between the first study-related procedure and within 30 days of the last dose of study medication will be reported. Adverse events will be reported to the Partners IRB according to guidelines.

Subjects should report any adverse events voluntarily or in response to general, non-directed questioning (e.g., "How has your health been since the last visit?). For each adverse event reported by the subject, the investigator should obtain all the information required to complete documentation in the subject's research file.

All adverse events, regardless of seriousness, severity, or presumed relationship to study therapy, must be recorded using medical terminology in the subject's study documents. Whenever possible, diagnoses should be given when signs and symptoms are due to a common etiology (e.g., cough, runny nose, sneezing, sore throat, and head congestion should be reported as "upper respiratory infection"). The investigator must document his/her opinion concerning the relationship of the adverse event to the study medication. All measures required for adverse event management must be recorded in the source document.

## **VIII. POTENTIAL BENEFITS**

Subjects will receive suvorexant, which may help their condition. They may benefit from the sleep diaries, actigraphy, review of symptoms, and regular discussions with the study doctor. Their participation in this study may help other people with RLS and insomnia by adding to the knowledge about this drug, and whether it is a beneficial treatment.

## IX. BIOSTATISTICAL ANALYSIS

Analysis of all study data will be conducted by [name]. All study personnel and participants will remain blinded to treatment assignment, including staff entering study data. Only the hospital Research Pharmacist who generates the randomization code will be unblinded to treatment assignment. The final database will not be unblinded until a medical and scientific review, protocol violators have been identified, and all study data are complete.

## **Overview of analytic plan:**

The primary hypothesis for this trial is that suvorexant is superior to placebo in reducing actigraphically-derived total sleep time in patients with persistent insomnia in the context of effectively treated restless legs syndrome. The primary endpoint is the change in actigraphically-derived total sleep time from baseline to the end of each 4-week treatment period. Key secondary endpoints include actigraphically-derived wake after sleep onset and self-reported ISI, and exploratory endpoints include subjective total sleep time and wake after sleep onset, and RLS severity.

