Suvorexant provides an important therapeutic option to treat insomnia in the context of RLS. It has demonstrated long-term efficacy, particularly in shortening the duration of nocturnal awakenings and increasing total sleep time. Similarly, it has a comparatively benign side effect profile compared to many of the agents described above.

Orexin is thought to play a key role in the central regulation of arousal which accounts for its benefits in insomnia. RLS, like insomnia, has been associated with hyperarousal. Whether orexin plays a specific role in RLS-related sleep disturbance is unclear. Two previous studies have examined orexin levels in RLS patients, with conflicting results.

To summarize, the proposed study is not to treat RLS but rather to address the substantial proportion of RLS patients whose core RLS symptoms are effectively managed by medications but are left with persistent insomnia. Clinically significant RLS is present in 3% of adults, roughly one-half of whom have control of core RLS symptoms with treatment. Over half of these patients report persistent insomnia, even with substantial control of their RLS symptoms, due to the limitations of current RLS medications. Thus, roughly 0.5-1% of adults have persistent insomnia with effectively treated RLS. Existing insomnia treatments can either worsen underlying RLS or lead to complex sleep-related behaviors or other side effects in this primarily older population. Suvorexant provides a potentially important option due to its efficacy and tolerability profile.

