## **II. SPECIFIC AIMS**

## Primary Aim:

• To determine whether suvorexant will have significantly greater effect than placebo in increasing actigraphically-derived total sleep time (TST) in patients with effectively treated restless legs syndrome (RLS) with persistent insomnia.

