## Secondary Aims:

- To determine whether suvorexant will have significantly greater effect than placebo in reducing actigraphically-derived wake after sleep onset (WASO) in patients with effectively treated RLS with persistent insomnia.
- To determine whether suvorexant will have significantly greater effect than placebo in decreasing Insomnia Severity Index (ISI) scores in patients with effectively treated RLS with persistent insomnia.

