## **Power/Sample Size:**

Statistical power for the primary endpoint, actigraphically-assessed total sleep time, was estimated from pooled analyses of data from placebo-controlled clinical trials of suvorexant for the treatment of insomnia using polysomnographically-measured total sleep time. The difference between 15/20 mg suvorexant and placebo at 1 month in least squares mean change from baseline was 34.7 minutes (95% CI: 27.8, 41.5), corresponding to an effect size of 0.58. Although actigraphy is not identical to polysomnography, multiple studies (including one by our group and two using the Phillips Spectrum actiwatch) with insomnia patients demonstrate high correlations between these two objective recording methods for total sleep time, wake after sleep onset, and sleep efficiency, particularly when event markers are employed.

With an effect size of .58, 34 randomized subjects are required to achieve 90% power to detect a statistical significance level of 0.05. In total, we expect to randomize 44 participants to treatment to have 34 completed subjects with evaluable data.

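### Does stating the primary hypothesis as a reduction in total sleep time put the primary analysis at risk?

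*Combined protocol and SAP*

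**What the plan says.** The Overview of analytic plan opens Section IX's account of the analysis with: "The primary hypothesis for this trial is that suvorexant is superior to placebo in reducing actigraphically-derived total sleep time". The next sentence defines the primary endpoint as the change in that measure from baseline to the end of each treatment period and gives no direction.

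Elsewhere the documents point the other way. The Primary Aim asks whether "suvorexant will have significantly greater effect than placebo in increasing actigraphically-derived total sleep time (TST"). The Background describes the drug's efficacy as lying "particularly in shortening the duration of nocturnal awakenings and increasing total sleep time". The Power/Sample Size section plans on a difference between suvorexant and placebo whose "least squares mean change from baseline was 34.7 minutes (95% CI: 27.8, 41.5").

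The first Secondary Aim does use the verb of reduction, correctly, for a different outcome: "suvorexant will have significantly greater effect than placebo in reducing actigraphically-derived wake after sleep onset (WASO").

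On the test itself, Statistical Methods says: "A two-sided P value <0.05 will be considered significant".

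**The concern.** The primary hypothesis is the claim against which the main result is read, and the only sentence carrying that label names the wrong direction. Taken literally, longer sleep on suvorexant would count against the hypothesis, and shorter sleep in people with insomnia would count as superiority.

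The analysis text does not put this right in words. Neither Study endpoints nor Statistical Methods states the order of subtraction between treatments or says which sign favours the drug. If the test were one-sided, or if a success rule referred to the hypothesis as worded, the slip could defeat the primary analysis. A direction corrected only after unblinding might also look as though it had been chosen to fit the data. So it is worth checking whether anything depends on the word.

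**Working it through.** **1. What each place says about direction**

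| Place | Outcome | Direction |
|---|---|---|
| Background | total sleep time | increase |
| Primary Aim | actigraphic total sleep time | increase |
| Power/Sample Size | total sleep time, change from baseline | difference of 34.7 min, interval 27.8 to 41.5, both limits positive |
| First Secondary Aim | actigraphic wake after sleep onset | reduction |
| Overview of analytic plan | actigraphic total sleep time | reduction |

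The last row stands alone. The Power/Sample Size section gives no order of subtraction, but it cites the same pooled analysis (reference 21) that the Background cites for increased sleep time, so the 34.7 minutes can only sensibly be a gain on suvorexant. The inclusion criteria, which require reported sleep of 7 hours or less, fit the same reading. The verb in the last row is the one that belongs to wake after sleep onset, which suggests a carry-over.

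**2. Where a direction could enter the analysis**

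- Endpoint: change from baseline, unsigned.
- Model: analysis of variance with treatment, sequence and period as fixed effects and subject within sequence as random. It yields a least squares mean treatment difference D with standard error SE.
- Decision: two-sided at 0.05, that is, reject when |D/SE| exceeds the critical value. Replacing D by -D leaves |D/SE|, and so the p-value, unchanged.
- Study endpoints mentions hierarchical testing, but Statistical Methods sets out no hierarchy or success rule that refers to a direction.

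**3. The plan's own sample size**

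Inputs from Power/Sample Size and Statistical Methods: effect size 0.58, power 90%, two-sided alpha 0.05. Assumption: 0.58 is the standardised within-subject difference. The implied standard deviation, 34.7 / 0.58 = 59.8 minutes, is not stated in the documents.

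- Normal approximation: n = ((1.960 + 1.282) / 0.58)² = 31.2, rounded up to 32.
- Noncentral t, n = 34: noncentrality 0.58 × √34 = 3.38. Power is 0.906 with 32 degrees of freedom (two-sequence crossover) and 0.907 with 33 (paired t).
- Noncentral t, n = 33: power 0.897 and 0.898.

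So 34 is the smallest number that reaches 90%, as the plan states.

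**4. The same calculation with the sign reversed**

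With -0.58 the noncentrality is -3.38 and the two-sided power is again 0.906 and 0.907. This equality follows from symmetry and holds whatever the correct standardisation of 0.58 may be.

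**5. When the word would matter**

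If a reduction were tested literally, one-sided at 0.025, with a true effect of +0.58 and 34 subjects, power would be about 8 × 10⁻⁸. The plan specifies no such test.

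**The case for a change.** The best case for acting is that a labelled primary hypothesis should be right as it stands. The sentence is current text and has no other grammatical reading. Within Section IX it is the only verbal statement of direction for this endpoint, so a reader must go back to the Primary Aim or infer the direction from the planning figure. The wording could be copied into a report, and changing one word costs nothing.

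Most of this stands as a description: the word is wrong, and no other sentence expressly corrects it. What does not stand is the consequence. Any harm requires someone to carry the sentence forward while ignoring the Primary Aim, which gives the same endpoint, comparator and population with the right direction. The worry about a direction fixed after the data are seen also fails, because the Primary Aim and Background already state it. A sign convention for the least squares mean difference would be tidy, but suvorexant minus placebo is what an analyst would use and label by default.

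**Conclusion.** The sentence contains a clerical slip, and no change to the plan follows. The size of the effect is zero for the estimate, the p-value, the 34 evaluable and 44 randomised subjects, and the power. The interpretation is also safe, because the Primary Aim fixes the intended direction and superiority over placebo in treating insomnia cannot sensibly mean shorter sleep.

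This rests on two features of the plan as written: significance is two-sided, and no decision rule refers to the direction in the hypothesis sentence. The power figures additionally assume that 0.58 is a within-subject standardised difference. They are given only to show that the sign makes no difference, and they do not endorse that effect size for a crossover design, which is a separate question.
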